14.2. Sample Size Justification

The plan is to enroll 170 subjects with a target of at least 153 subjects to complete. No historical 2 by 2 crossover study was available to estimate the treatment difference of the primary and secondary endpoints between the Test (AO1DfA) and the Control (AO1D) on the study population. The Visual Performance HLHC logMAR and Contact Lens Preference from [REDACTED] between 1-Day ACUVUE® Moist Astigmatism and 1-Day ACUVUE® Moist were summarized in Table 7. These estimates are used as references to estimate the power for the primary hypothesis in Table 8 and for the third secondary hypothesis (S3) in Table 11. Due to the lack of historical data, several scenarios are enumerated to estimate the power for the first secondary hypothesis (S1) in Table 9 and similarly for second secondary hypothesis (S2) in Table 10. Scenarios with above 80% power is highlighted in blue. The power calculations were conducted with paired t test for the primary, first and second secondary hypotheses; and with Pearson's chi-square test for the third hypothesis using the POWER procedure in SAS 9.4.

Table 7: Historical Data from [REDACTED]

Endpoint	N Subjects	1-Day ACUVUE® Moist for Astigmatism	1-Day ACUVUE® Moist	Intraclass Correlation
Visual Performance (HLHC logMAR)	72	Mean (SD) -0.09 (0.08)	Mean (SD) -0.02 (0.09)	0.399
Contact Lens Preference	72	N (%) 49 (68.1%)	N (%) 17 (23.6%)	-

Clinical Study Protocol
Johnson & Johnson Vision Care, Inc.

Table 8: Power Calculation for the Visual Performance (HLHC logMAR) for the primary hypothesis with Type I error of 0.05.

Mean Difference (Test - Control)	Standard Deviation	Total Sample Size (n/2 per sequence)	Intraclass Correlation		
			0.3	0.4	0.5
-0.025	0.09	153	0.823	0.876	0.927
-0.070	0.09	153	0.999	0.999	0.999

Table 9: Power of the First Secondary Hypothesis of CLUE Vision score for the first secondary hypothesis (S1) with Type I error of 0.05.

Mean Difference (Test - Control)	Standard Deviation	Total Sample Size (n/2 per sequence)	Intraclass Correlation		
			0.4	0.5	0.6
4	18	153	0.703	0.780	0.863
4	20	153	0.612	0.691	0.785
4	22	153	0.532	0.608	0.705
5	18	153	0.876	0.927	0.968
5	20	153	0.801	0.867	0.930
5	22	153	0.722	0.798	0.878

Table 10: Power of the Visual Performance (HLHC logMAR) for the second secondary hypothesis (S2).

Mean Difference (Test - Spectacles)	Type I Error	Standard Deviation	Total Sample Size (n/2 per sequence)	Intraclass Correlation		
				0.3	0.4	0.5

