0.015	0.025	0.09	153	0.992	0.998	0.999
0.015	0.05	0.09	153	0.997	0.999	0.999
0.030	0.025	0.09	153	0.703	0.780	0.863
0.030	0.05	0.09	153	0.803	0.862	0.921

Table 11: Power Calculation for the Contact Lens Preference (superiority) for the third secondary hypothesis (S3).

	Type I Error	Total Sample Size	Proportion

Clinical Study Protocol
Johnson & Johnson Vision Care, Inc.

Proportion Difference (Test - Control)	(2-sided)	(n/2 per sequence)	(Prefer the Control)		
			0.3	0.4	0.5
0.24	0.025	153	0.782	0.771	0.797
0.24	0.05	153	0.858	0.849	0.869
0.32	0.025	153	0.965	0.966	0.979
0.32	0.05	153	0.983	0.983	0.990

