14.4. Level of Statistical Significance

The following graphical Gatekeeping strategy¹² will be used to control the overall study-wise two-sided type I error rate $\alpha=5\%$. The primary hypothesis will be conducted with the two-sided type I error rate of $\alpha=5\%$. If primary hypothesis is met, the first secondary hypothesis will be conducted with $\alpha=5\%$. If first secondary hypothesis (S1) is met, the second and third secondary hypothesis will be conducted with the α -propagation proposed in Figure 2 which is also the Holm procedure. For exploratory analyses, each analysis is conducted with two-sided type I error rate $\alpha=5\%$.

Clinical Study Protocol

Johnson & Johnson Vision Care, Inc.

Figure 2: Gatekeeping strategy and α -propagation, P1 – Primary hypothesis and S1-3 – the first to third secondary hypothesis defined in section 2.3.

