where Δ is the mean difference in logMAR between Test lens and Control lens (Test minus Control). Non-inferiority will be declared on Per-protocol population if the upper bound of the (1- α) two-sided confidence interval of the mean difference between Test and Control is less than 0.05. The α is the Type I error derived from Gatekeeping strategy and α -propagation in Section 14.4. If the non-inferiority is established, superiority will be declared

Clinical Study Protocol

Johnson & Johnson Vision Care, Inc.

if the upper bound of the confidence interval of the mean difference between Test and Control is less than 0.0.

Contact Lens Preference – (S3)

Contact lens preference question will be analyzed using a baseline-category logistic model, where the response of the Control lens preference is the baseline category. This model will include the experimental design factors: sequence of lens wear, lens wearing period, lens type and the interaction between lens type and lens wearing period as fixed effects. Baseline characteristics known of importance such as age and gender will be included as fixed covariates.

The null and alternative hypotheses for superiority of Test (AO1DfA) lens relative to Control (AO1D) are as follows:

$$H_0: \Delta \leq 1.0$$
$$H_A: \Delta > 1.0$$

where Δ is the odds of the preference for the Test to the preference for the Control (Test divided by Control). Superiority for the Test to the Control lens will be established on ITT population if the lower bound of the $(1 - \alpha)$ % two-sided confidence interval (CI) for least squares mean (LSM) odds (Test divided by Control) of the contact lens preference is greater than 1.0. The α is the Type I error derived from Gatekeeping strategy and α -propagation in Section 14.4.

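### Table 10 overstates power for the S2 non-inferiority test: it uses twice the one-sided alpha that Section 14.6 allows and correlations 0.1 above those printed, so under the stated rule and printed ICCs no 0.030 scenario reaches 80%

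*Combined protocol and SAP*

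**What the plan says.** Section 14.2 states the method: "The power calculations were conducted with paired t test for the primary, first and second secondary hypotheses", run in the SAS POWER procedure with 153 completers. The caption "Table 10: Power of the Visual Performance (HLHC logMAR) for the second secondary hypothesis (S2" heads a table of true differences (toric lens minus spectacles) of 0.015 and 0.030 logMAR. Each is shown at type I error 0.025 and 0.05, with SD 0.09 and ICC columns 0.3, 0.4 and 0.5. One row reads "0.030 0.025 0.09 153 0.703 0.780 0.863". Table 10 does not say whether its type I error is one- or two-sided, whereas Table 11 labels its own as two-sided. The section also says "Scenarios with above 80% power is highlighted in blue".

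Section 14.4 sets out to "control the overall study-wise two-sided type I error rate" at 5%. Once the primary hypothesis and S1 are met, S2 and S3 share that 5% through an alpha-propagation scheme "which is also the Holm procedure". S2 is therefore tested at a two-sided alpha of 0.025, or 0.05 if S3 has already been met.

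Section 14.6 declares S2 non-inferiority on the per-protocol population "if the upper bound of the (1- α) two-sided confidence interval of the mean difference between Test and Control is less than 0.05".

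**The concern.** Two things do not fit together.

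- **Alpha.** Comparing the upper bound of a two-sided interval at level 1 − alpha with the margin is a one-sided test at alpha/2. For S2 that is 0.0125 or 0.025, but Table 10 appears to put the whole 0.025 or 0.05 in one tail.
- **ICC.** The Table 10 row for difference 0.030 and alpha 0.025 is identical to the Table 9 row for a CLUE difference of 4 with SD 18. Table 9 heads those three powers 0.4, 0.5 and 0.6; Table 10 heads them 0.3, 0.4 and 0.5.

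Both discrepancies push the printed power upward. S2 is a confirmatory hypothesis inside the alpha-controlled family, and a reader would take from Table 10 that it is adequately powered in four of the six 0.030 scenarios.

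**Working it through.** **Inputs.** Paired t test, n = 153 (df = 152) and SD 0.09 from Section 14.2; margin 0.05 logMAR and the interval rule from Section 14.6; alpha 0.025 or 0.05 from Section 14.4.

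**Formulas.**
- SD of the paired difference = SD × √(2(1 − ICC))
- Noncentrality = (0.05 − true difference) ÷ SD of difference × √153
- Power = P(noncentral t with 152 df > critical t)

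**Step 1. Check the method on the neighbouring tables.** At two-sided 0.05, Table 8 for a difference of −0.025 gives 0.823/0.876/0.927 at ICC 0.3/0.4/0.5, as printed. Table 9 for difference 4, SD 18 gives 0.703/0.780/0.863 at ICC 0.4/0.5/0.6, as printed, and the other Table 9 rows match too. The only departure is in Table 8's −0.070 row, which prints 0.999 where the value is 1.000 to three decimals. This looks like a display cap.

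**Step 2. The ICC shift is visible without software.** For difference 0.030 the standardised distance to the margin is (0.05 − 0.030)/0.09 = 0.222. In Table 9, 4/18 = 0.222. Sample size is the same, and a two-sided 0.05 test has the same upper tail (0.025) as a one-sided 0.025 test. Equal powers therefore require equal ICCs, yet the column headings differ by 0.1.

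**Step 3. Reproduce Table 10 at difference 0.030.** The distance to the margin is 0.020. Critical t values are 2.264, 1.976 and 1.655 for one-sided 0.0125, 0.025 and 0.05.

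| ICC | SD of difference | Noncentrality | Power, one-sided 0.0125 | Power, one-sided 0.025 | Power, one-sided 0.05 |
|---|---|---|---|---|---|
| 0.3 | 0.1065 | 2.323 | 0.525 | 0.636 | 0.748 |
| 0.4 | 0.0986 | 2.509 | 0.598 | 0.703 | 0.803 |
| 0.5 | 0.0900 | 2.749 | 0.686 | 0.780 | 0.862 |
| 0.6 | 0.0805 | 3.073 | 0.790 | 0.863 | 0.921 |

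The printed rows (0.703/0.780/0.863 and 0.803/0.862/0.921) are the one-sided 0.025 and 0.05 columns at ICC 0.4, 0.5 and 0.6. At the printed ICCs, even with the full alpha in one tail, the values would be 0.636/0.703/0.780 and 0.748/0.803/0.862. The 0.015 rows match the same shifted ICCs (0.992/0.998/0.9996 and 0.997/0.999/0.9999), allowing for the 0.999 cap.

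**Step 4. Apply the Section 14.6 rule (one-sided alpha/2) at the printed ICCs 0.3/0.4/0.5.**

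| True difference | Alpha (two-sided) | Printed | Under the stated rule |
|---|---|---|---|
| 0.015 | 0.025 | 0.992/0.998/0.999 | 0.963/0.983/0.994 |
| 0.015 | 0.05 | 0.997/0.999/0.999 | 0.981/0.992/0.998 |
| 0.030 | 0.025 | 0.703/0.780/0.863 | 0.525/0.598/0.686 |
| 0.030 | 0.05 | 0.803/0.862/0.921 | 0.636/0.703/0.780 |

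The largest gap is 0.780 − 0.598 = 0.182. For a 0.030 difference, 80% power would need 272/234/195 completers at alpha 0.025, or 225/193/161 at alpha 0.05, against the 153 planned.

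**The case against.** The arithmetic is hard to dispute; the case against concerns what follows from it.

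- **Which part is wrong, headings or values?** The documents do not say. If ICCs of 0.4, 0.5 and 0.6 were intended, correcting alpha alone gives 0.598/0.686/0.790 and 0.703/0.780/0.863, so one of the six 0.030 cells passes 80%. If only the ICCs are corrected, two pass (0.803 and 0.862 at alpha 0.05). This stands: the statement that no 0.030 scenario reaches 80% needs both corrections, and it takes the headings as meant. The headings are the plan's own statement, and the only historical HLHC ICC, 0.399 in Table 7, falls on the printed 0.4 column.
- **Alpha as a labelling gap.** Read as one-sided, the 0.025 rows do describe the full-alpha Holm step. But the 0.05 rows then match no S2 step, and the 0.0125 step is missing.
- **Consequences are limited.** The decision rule and error control are sound, the primary and S1 tables are correct, study success rests on the primary hypothesis, and Section 14.2 offers scenarios without promising 80% for S2. All true. This bounds the damage but does not make the table right.
- **Paired t versus the planned model.** The actual analysis is a mixed model on monocular acuity, whose power could be higher or lower. The corrected figures are therefore power under the plan's own stated method.
- **Highlighting.** The blue shading cannot be seen in the text available, so which cells carry it is unconfirmed.

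**Conclusion.** The concern holds. Table 10 was computed with the full alpha in one tail and at ICCs of 0.4, 0.5 and 0.6, neither of which agrees with Section 14.6 or with its own headings. Under the stated rule and printed ICCs, power at a true difference of 0.030 is overstated by 14 to 18 percentage points, and all four cells printed above 80% drop below it; the highest is 0.780. At the ICC nearest the historical value (0.4), power is 0.598 or 0.703, against 0.780 or 0.862 printed. The 0.015 scenarios are little affected, with a minimum of 0.963.

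These figures assume the paired t test, SD 0.09 and 153 analysable subjects. S2 uses the per-protocol population, which may be smaller; that would lower power further.

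**What to change.** Replace Table 10 with power at one-sided alpha/2 (0.0125 and 0.025) for ICC 0.3, 0.4 and 0.5, using the right-hand column of the last table in the working. Label the alpha as two-sided, as Table 11 does, and remove any above-80% highlighting from the 0.030 rows. The sponsor should confirm that the printed ICCs are the intended ones. If 0.4, 0.5 and 0.6 were meant, the headings must change as well, and the 0.030 rows become 0.598/0.686/0.790 and 0.703/0.780/0.863.

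The cost is one table and one sentence in Section 14.2, plus a less favourable power statement for S2. Sample size, margin, hypothesis and analysis stay as they are.

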14.3. Analysis Populations

Safety Population:

All subjects who are administered any test article excluding subjects who drop out prior to administering any test article. At least one observation should be recorded.

Per-Protocol Population:

All subjects who successfully complete all visits and do not substantially deviate from the protocol as determined by the trial cohort review committee prior to database hard lock. Justification for the exclusion of subjects with protocol deviations from the per-protocol population set will be documented in a memo to file.

Intent-to-Treat (ITT) Population:

All randomized subjects regardless of actual treatment and subsequent withdrawal from the study or deviation from the protocol. At least one observation should be recorded.

[figure not shown]
14.4. Level of Statistical Significance

The following graphical Gatekeeping strategy¹² will be used to control the overall study-wise two-sided type I error rate $\alpha=5\%$. The primary hypothesis will be conducted with the two-sided type I error rate of $\alpha=5\%$. If primary hypothesis is met, the first secondary hypothesis will be conducted with $\alpha=5\%$. If first secondary hypothesis (S1) is met, the second and third secondary hypothesis will be conducted with the α -propagation proposed in Figure 2 which is also the Holm procedure. For exploratory analyses, each analysis is conducted with two-sided type I error rate $\alpha=5\%$.

Clinical Study Protocol

Johnson & Johnson Vision Care, Inc.

Figure 2: Gatekeeping strategy and α -propagation, P1 – Primary hypothesis and S1-3 – the first to third secondary hypothesis defined in section 2.3.

14.5. Primary Analysis

The primary analyses will be conducted on Intent-to-Treat populations to establish superiority.

Visual Performance (HLHC logMAR)

Monocular distance visual performance of HLHC in logMAR scale will be analyzed using a linear mixed effect model. This model will include the experimental design factors: sequence of lens wear, lens wearing period, lens type and the interaction between lens type and lens wearing period as fixed effects. Baseline characteristics known of importance such as age and gender will be included as fixed covariates. Site will be included as random effects (G-side). The covariance of residuals between of the same subject (R-side) across period will be modeled using either homogenous compound symmetry (CS), heterogeneous compound-symmetry (HCS) or unstructured (UN) covariance structure. The structure that returns the lowest finite sample corrected Akaike's Information criterion¹⁰ will be selected as the structure that best fits the model. The Kenward and Roger method will be used for the calculation of the denominator degree of freedom¹¹.

The null and alternative hypotheses for superiority of Test (AO1DfA) lens relative to Control (AO1D) are as follows:

$$H_0: \Delta \geq 0.0$$
$$H_A: \Delta < 0.0$$

where Δ is the mean difference in logMAR between Test and Control lens (Test minus Control). Superiority for the Test to the Control lens will be established on ITT population if the upper bound of the 95% two-sided confidence interval (CI) for least squares mean (LSM) difference (Test - Control) of HLHC logMAR is less than 0.

Clinical Study Protocol

Johnson & Johnson Vision Care, Inc.

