3.7	Distance ETDRS visual acuity	
Measure monocular distance high-luminance, high-contrast (HLHC) and high-luminance, low-contrast (HLLC) visual acuity using ETDRS charts at 4 meters.
 
Measure each eye using the charts shown in the table below:
 
  
 Condition	HLHC	HLLC	
   
 Room illumination	> 400 lux	
 
 Chart luminance	120 - 200 cd/m²	
 
 Eye	OD	OS	OD	OS	
 
 Charts	HC-1	HC-2	LC-1	LC-2	
  
 
Recorded letter-by-letter results into EDC.
	Condition	HLHC	HLLC	Room illumination	> 400 lux		Chart luminance	120 - 200 cd/m ²		Eye	OD	OS	OD	OS	Charts	HC-1	HC-2	LC-1	LC-2	
Condition	HLHC	HLLC																				
Room illumination	> 400 lux																					
Chart luminance	120 - 200 cd/m ²																					
Eye	OD	OS	OD	OS																		
Charts	HC-1	HC-2	LC-1	LC-2																		
3.8	Toric lens orientation (for toric lenses only)	Measure toric lens orientation for each eye using a slit lamp biomicroscope and record to the nearest degree.																				

Clinical Study Protocol
Johnson & Johnson Vision Care, Inc.

Visit 3: Follow-up #1		
Step	Procedure	Details
3.9	General lens fit assessment	
The fitting characteristics of the lens in both eyes will be assessed using a slit lamp. Lens position (centration, limbal exposure, edge lift) and movement (primary and up gaze as well as push-up) will be assessed. Fit acceptability is defined as any lens that does not display the following general fit characteristics:
 
 • Limbal exposure (presence of clear cornea) in any direction of gaze. • Edge lift • Insufficient movement in all three movement assessments (primary gaze, up-gaze and push-up test). • Excessive movement in primary gaze
3.10	Lens removal	
Remove and place both lenses into a lens case with saline solution.
 
Do not discard the lenses until after biomicroscopy has been completed.

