4.6	Distance ETDRS visual acuity	
Measure monocular distance high-luminance, high-contrast (HLHC) and high-luminance, low-contrast (HLLC) visual acuity using ETDRS charts at 4 meters with the subject wearing the habitual spectacle correction.
 
Measure each eye using the charts shown in the table below:
 
  
 Condition	HLHC	HLLC	
   
 Room illumination	> 400 lux	
 
 Chart luminance	120 - 200 cd/m²	
 
 Eye	OD	OS	OD	OS	
 
 Charts	HC-1	HC-2	LC-1	LC-2	
  
 
Recorded letter-by-letter results into EDC.
			Condition	HLHC	HLLC	Room illumination	> 400 lux		Chart luminance	120 - 200 cd/m ²		Eye	OD	OS	OD	OS	Charts	HC-1	HC-2	LC-1	LC-2
Condition	HLHC	HLLC																					
Room illumination	> 400 lux																						
Chart luminance	120 - 200 cd/m ²																						
Eye	OD	OS	OD	OS																			
Charts	HC-1	HC-2	LC-1	LC-2																			
4.7	Biomicroscopy	
The FDA Slit Lamp Classification Scale will be used to grade findings. If any slit lamp finding is graded as 3 or worse, the subject must be discontinued, an adverse event will be recorded, and the subject will be monitored as per the guidelines given in section 13.
 
Should the clearance of the fluorescein need to be expedited, preservative free rewetting drops or artificial tears may be instilled.
																					
4.8	Continuance	Verify that the subject is eligible to continue in the study.																					

Visit 4: Lens Fitting #2

The steps followed will be the same as those listed under Visit 2: Lens fitting #1.

Clinical Study Protocol

Johnson & Johnson Vision Care, Inc.

VISIT 5

Visit 5 will occur 5 to 9 days following Visit 4. Subjects must present to this visit wearing the study lenses in both eyes, and lenses must have been worn for at least 1 hour prior to the visit.

Subjects should bring their own habitual spectacles or contact lenses to this visit to wear following study lens removal.

Visit 5: Follow-up #2		
Step	Procedure	Details

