14. STATISTICAL METHODS

14.1. General Considerations

Statistical Analysis will be undertaken by the sponsor or under the authority of the sponsor. A general description of the statistical methods to be implemented in this clinical trial is outlined below.

All data summaries and statistical analyses will be performed using the Statistical Analysis System (SAS) software Version 9.4 or higher (SAS Institute, Cary, NC). Throughout the analysis of data, the results for each subject/eye will be used when available for summarization and statistical analysis. Unscheduled visits will be summarized separately and will be excluded from the statistical analysis.

Summary tables (descriptive statistics and/or frequency tables) will be provided for all baseline variables, efficacy variables and safety variables as appropriate. Continuous variables will be summarized with descriptive statistics (n, mean, standard deviation (SD), median, minimum and maximum). Frequency count and percentage of subjects or eyes within each category will be provided for categorical data.

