14.6. Secondary Analyses

The secondary analyses will be conducted on Intent-to-Treat populations to establish superiority and Per-protocol populations for non-inferiority.

CLUE Vision score – (S1)

CLUE vision scores at 1-week follow-up will be analyzed using a linear mixed effect model. This model will include the experimental design factors: sequence of lens wear, lens wearing period, lens type and the interaction between lens type and lens wearing period as fixed effects. Baseline characteristics known of importance such as age and gender will be included as fixed covariates. Site will be included as random effects (G-side). The covariance of residuals between of the same subject (R-side) across period will be modeled using either homogenous compound symmetry (CS) or unstructured (UN) covariance structure. The structure that returns the lowest finite sample corrected Akaike's Information criterion¹⁰ will be selected as the structure that best fits the model. The Kenward and Roger method will be used for the calculation of the denominator degree of freedom¹¹.

The null and alternative hypotheses for superiority of CLUE Vision for the Test (AO1DfA) minus Control (AO1D) is as follows:

$$H_0: \Delta \leq 0.0$$
$$H_A: \Delta > 0.0$$

where Δ is the least-square means (LSM) difference between the Test and Control lens (Test minus Control). Superiority for the Test to the Control lens will be established on ITT population if the lower bound of the 95% two-sided confidence interval (CI) for least squares mean (LSM) difference (Test - Control) of CLUE Vision score is greater than 0.

Visual Performance (HLHC logMAR) – (S2)

The comparison of Monocular distance visual performance of HLHC in logMAR scale between the Test (AO1DfA) to the Control (Spectacles) will be analyzed using a similar linear mixed effect model described in the primary analysis above. Since this endpoint for the Test lens (AO1DfA) will be collected before or after the Control (Spectacles) and no carryover effect is expected in objective visual performance, the lens wearing period can be defined accordingly.

The null and alternative hypotheses for non-inferiority of Test lens (AO1DfA) relative to Control (Spectacles) are as follows:

$$H_0: \Delta > 0.05$$
$$H_A: \Delta \leq 0.05$$

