14.9. Procedure for Handling Missing Data and Drop-Outs

Missing or spurious values will not be imputed. The count of missing values will be included in the summary tables and listings.

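### Does leaving the handling of a subject's two eyes unstated put the primary and S2 confidence intervals at risk?

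*Combined protocol and SAP*

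**What the plan says.** Section 7.2 obtains two acuity values at each relevant visit. For Visits 3 and 5 the instruction is "Measure each eye using the charts shown in the table below", with separate charts for OD and OS, and Visit 4 does the same in spectacles. Section 14.1 adds that "the results for each subject/eye will be used when available for summarization and statistical analysis".

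Section 14.5 says "Monocular distance visual performance of HLHC in logMAR scale will be analyzed using a linear mixed effect model". The fixed effects are sequence, period, lens, lens by period, and covariates such as age and gender. Site is the only random effect. Within-subject dependence is carried by one sentence, "The covariance of residuals between of the same subject (R-side) across period will be modeled using either homogenous compound symmetry (CS", which goes on to name heterogeneous compound symmetry (HCS) and unstructured (UN) as the other candidates. The lowest corrected AIC decides. For S2, section 14.6 says the spectacle comparison "will be analyzed using a similar linear mixed effect model described in the primary analysis above".

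Nothing states that the eyes are averaged, that one eye is chosen, or how eye is indexed in the residual matrix. On sample size, section 14.2 says "The power calculations were conducted with paired t test for the primary, first and second secondary hypotheses". Section 14.9 says "Missing or spurious values will not be imputed".

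**The concern.** Each subject contributes up to four values to the primary contrast, two eyes under two lenses, and fellow eyes are not independent. The variance of the lens difference depends on how that dependence is modelled, and section 14.5 refers only to correlation across periods. If a programmer made each eye its own block, the interval would be too narrow whenever the two eyes respond alike. If a single correlation were forced on all four records, the interval could be too narrow or too wide.

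The primary interval decides whether the study succeeds and opens the gate to S1, S2 and S3. S2 inherits the model and is judged against a 0.05 logMAR margin. Too narrow an interval would raise the rates of false superiority and false non-inferiority.

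**Working it through.** **1. The plan's own figure.** Table 8: N = 153, SD 0.09, difference -0.025, two-sided 0.05. With one difference per subject, the SD of the difference is 0.09 × √(2(1 − ICC)). At ICC 0.4 this is 0.0986, the standard error is 0.0986/√153 = 0.00797, and the ratio is 0.025/0.00797 = 3.14. The noncentral t gives power 0.823/0.876/0.927 at ICC 0.3/0.4/0.5, as printed. Counting 306 eyes as independent pairs would give 0.984/0.993/0.998. The planning unit is therefore the subject.

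**2. Notation (assumed; not in the documents).** Equal variances. f = correlation of fellow eyes in the same period, s = same eye across periods, c = opposite eyes across periods. The true variance of the eye-averaged lens difference is proportional to 1 + f − s − c.

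**3. Eye as its own block.** This assumes 1 − s, so true/assumed = 1 + r, with r = (f − c)/(1 − s). Two-sided error = 2(1 − Φ(1.96/√(1 + r))): 0.074, 0.098 and 0.110 at r = 0.2, 0.4 and 0.5. For S2 at the first Holm step, 1 − Φ(2.241/√(1 + r)) = 0.020, 0.029 and 0.034 against 0.0125. This coding is not open under section 14.5, which places the covariance within the subject.

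**4. HCS or UN indexed by period alone.** Two records share each period, so the matrix implies a fellow-eye correlation of 1 and has rank 2 of 4. It cannot be fitted, so it cannot mislead.

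**5. Four records per subject.** A single CS assumes 1 − (f + s + c)/3. With f = 0.6, s = 0.4, c = 0.3, the true value is 0.9, the assumed value is 0.567 and the ratio is 1.59. The error is 2(1 − Φ(1.96/1.26)) = 0.120. But the plan does not fix CS; it lets corrected AIC choose among CS, HCS and UN. Simulated two-sided error under that rule (153 subjects, REML, 2,000 trials per setting, Monte Carlo SE about 0.005):

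| f / c (s = 0.4) | CS alone (formula) | After AICc choice | UN chosen | OD/OS mean |
|---|---|---|---|---|
| 0.20 / 0.20 | 0.030 | 0.051 | 70% | 0.056 |
| 0.42 / 0.30 | 0.068 | 0.064 | 35% | 0.054 |
| 0.45 / 0.35 | 0.070 | 0.057 | 20% | 0.047 |
| 0.54 / 0.30 | 0.101 | 0.065 | 98% | 0.057 |
| 0.60 / 0.30 | 0.120 | 0.051 | 100% | 0.052 |

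Where CS would do most harm, the selection rule rejects it. Smaller repeat runs agree. One set gave 0.043 at 0.5/0.3 and 0.046 at 0.6/0.3 (600 and 800 trials). Another gave 0.053 to 0.073 over its settings, against 0.048 to 0.062 for the OD/OS mean (about 600 to 670 trials each, SE about 0.009).

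**6. What the text points to.** For CLUE vision, with one score per subject per period, section 14.6 lists only CS and UN. For monocular acuity, section 14.5 adds HCS. In a 2 × 2 matrix HCS and UN are the same model, so adding HCS has a purpose only with more than two records per subject. That favours the four-record block. The paired t test favours the OD/OS mean. Both are sound.

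**7. Effect on the decision.** At ICC 0.4 the standard error of the two-eye mean difference is 0.0056 at r = 0 and 0.0076 at r = 0.8. The Table 7 difference of -0.07 is then at least 0.070/0.0076 = 9.2 standard errors from zero.

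**The case for a change.** The strongest case for acting is that a confirmatory test should have its unit of analysis fixed before data are seen, and one sentence would do it. The CLUE model uses almost the same covariance wording for a one-record outcome, so that wording alone does not describe two eyes, and the HCS clue is an inference. The protocol also plans for a difference as small as -0.025 and had no historical crossover in these lenses, so the reassurance at -0.070 is not guaranteed to apply. Finally, with no imputation, a subject with one eye recorded would be handled differently under averaging and under an eye-level model.

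The omission stands as described. What does not follow is material harm. The large error rates need a coding that contradicts the within-subject block, or a CS structure used without the stated selection. The missing-eye point is fair but small: both eyes are tested in the same step of the same visit, so a lone missing eye should be uncommon, and no harm from it has been quantified.

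**Conclusion.** No change to the plan follows. Section 14.5, and S2 through it, leaves out whether the eyes are averaged or modelled as eye-by-period records within subject. The readings that respect the text and can be fitted are close to nominal: about 0.04 to 0.07 two-sided for the four-record block with AICc selection, and about 0.05 to 0.06 for the OD/OS mean. The highest simulated value, 0.073, corresponds to about 0.037 in the direction of the superiority claim against 0.025, and it comes from a small run.

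These sizes rest on assumed fellow-eye correlations, equal variances, and simulations without site or covariates that used a t reference with 151 degrees of freedom in place of Kenward-Roger. The sample size is unaffected, since Table 8 already rests on one difference per subject. This is a detail that a competent analyst would settle sensibly when programming the model.
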